6.15.1. Efficacy Subgroup Analysis

Subgroup analyses will be conducted for the following efficacy assessments:

- Clinical Remission at 12 weeks

Subgroups to be evaluated include the following:

- Patient Demographic Subgroups:
 - Gender: female or male
 - Age group: < 65 years, ≥65 years
 - Race: American Indian/Alaska Native, Asian, Black/African American, Native Hawaiian/Other Pacific Islanders, White, or Multiple Races
 - Ethnicity: Hispanic/Latino, Non-Hispanic/Non-Latino
 - Weight: <100 kg or ≥100 kg
 - Weight: <80 kg, ≥80 and <100 kg, or ≥ 100 kg

- Body mass index (BMI, kg/m^2) category (underweight ($<18.5 \text{ kg/m}^2$); normal (≥ 18.5 and $<25 \text{ kg/m}^2$); overweight (≥ 25 and $<30 \text{ kg/m}^2$); obese (≥ 30 and $<40 \text{ kg/m}^2$); or extreme obese ($\geq 40 \text{ kg/m}^2$))
- Geographic Region Subgroups:
 - Geographic region: North America, Asia (Japan) and Rest of World (incl. EU and Australia, NZ)
- Prior/Concomitant UC Therapy:
 - Prior Biologic therapy vs Biologic Naïve
 - Concomitant UC Baseline Medication:
 - Corticosteroid current use (concomitant use of any medications with ATC codes A07EA, H02AB, A01AC) vs none
 - 5 ASAs current use (concomitant use of any medications with ATC code A07EC) vs none
 - Thiopurines current use (e.g. azathioprine; concomitant use of any medications with ATC code L01BB, LO4AX (where Preferred name= “AZATHIOPRINE”)) vs none
 - More than one of the above
- Baseline Severity Groups:
 - Mayo score at baseline (6-8, 9-12)
 - CRP: 6 mg/L, $>6 \text{ mg/L}$
- Other Baseline Patient Characteristics Subgroups:
 - Smoking status at baseline: yes or no
- Therapeutic Drug Monitoring Subgroup
 - TDM adjustment status: yes or no

For Week 12 Clinical Remission analyses, a logistic regression model with treatment, subgroup, and the interaction of treatment-by-subgroup included as factors will be used. The treatment-by-subgroup interaction will be tested at the significance level of 0.10. Treatment group differences will be evaluated within each category of the subgroup using Fisher’s exact test, regardless of whether the interaction is statistically significant. Missing data will be imputed using NRI, as described in Section 6.4.1. If any group within the subgroup (for example, yes, no) is less than 10% of the total population, only descriptive statistics will be provided for that subgroup (that is, no inferential testing).

Prior Biologic UC Therapy may be summarized using ATC codes L04AA, L04AB, A07E (where preferred name="ETROLIZUMAB"). Prior Biologic use status for the purposes of subpopulation identification will be based on the 'Prior Biologic Y/N?' eCRF question.

TDM adjustment status will be determined by utilizing responses in the Exposure Based Dose Adjustment eCRF page.

Additional subgroup analyses may be performed as deemed necessary.

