7.1. Summary of Study Design

Study I6T-MC-AMAC is a multicenter, randomized, double-blind, parallel-arm, placebo-controlled trial in which approximately 240 subjects will be randomized (Figure AMAC.7.1). Subjects must have moderate or severe UC (defined as a Mayo score of 6 to 12 with an endoscopic subscore ≥ 2 ; see Attachment 5). Approximately two-thirds (~160) of the subjects randomized to study treatment must have been exposed to at least 1 previous biologic therapy (received treatment with 1 or more agents such as tumor necrosis factor [TNF] antagonists, vedolizumab, or experimental UC biologic therapy), and approximately one-third (~80) of the subjects will be naive to biologic therapy.

All procedures to be conducted during the study, including timing of all procedures, are indicated in the study schedule (Attachment 1).

Screening Period

Subjects will be evaluated for study eligibility ≤ 28 days before the baseline visit. At the baseline visit, subjects who fulfill the eligibility criteria will be randomized equally to 1 of 4 induction treatment arms.

Subjects may be rescreened upon review and consultation with a member of the Lilly medical team.

Induction Period

A 12-week induction period is designed to establish the efficacy and safety of LY3074828 administered IV at Weeks 0, 4, and 8 (described in Section 10.1 and Section 10.3, respectively). Approximately 240 subjects will be enrolled into 4 induction treatment arms (placebo or 50 mg, 200 mg, or 600 mg of LY3074828) to adequately evaluate the clinical response and remission endpoints. On the basis of plasma concentrations of LY3074828 during the induction period, dose levels in individual subjects within the 50-mg and 200-mg arms may be increased (Section 9.1) and will be communicated to the site by the sponsor. The 600-mg dose arm will remain at a fixed dose during the induction period. No subject will be dosed above 600 mg in this initial induction period. Subjects enrolled in the trial will be stratified across the treatment arms on the basis of previous exposure to biologic therapy for treatment of UC.

Subjects who discontinue the study for any reason before the end of the induction period will complete the induction period early termination visit (V7).

Maintenance Period:

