9.5. Therapeutic Drug Monitoring and Dose Adjustment

Experience with use of anti-TNF antibodies in treating IBD suggests that inadequate drug exposure in some subjects may be a factor contributing to lack of efficacy (Ordás et al. 2012b). The application of therapeutic drug monitoring and dose adjustment may therefore result in a higher probability of response in individual subjects who have low exposure and improved overall response rates.

Exposure-Based Dose Adjustment

In this study, subjects in the 50- and 200-mg dose groups will have their doses increased at the Week 4 (Day 29) and Week 8 (Day 57) visits if the projected trough concentrations for those visits fall below prespecified thresholds. The concentration thresholds selected for the 50- and 200-mg arms are 0.5 and 2.0 µg/mL, respectively. The concentrations of 0.5 and 2.0 µg/mL are not related to expected efficacy at these specific target concentrations but rather were selected so that only the subjects with lower than expected exposures in the 50- and 200-mg groups would have their doses increased. On the basis of PK simulations, these thresholds are estimated to result in dose increases in approximately 40% of subjects at Week 4. A smaller percentage of subjects are expected to require dose adjustment at Week 8.

The projected trough concentration for an individual subject will be estimated on the basis of concentration data collected before the date when doses will be adjusted. Application of exposure-based dose adjustment in this study will only serve to increase the dose level if drug concentrations are below the prespecified thresholds. Dose level will not be reduced on the basis of drug concentrations, and once a subject has a dose level increase, the dose will not be reduced. Dose adjustments on the basis of drug concentration levels will only be done during the induction period.

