Age, sex and race will be reported on all by-patient listings unless otherwise specified. Sex will be abbreviated as follows: female (F) and male (M). Race will be abbreviated as follows: American Indian or Alaska Native (AI), Asian (AS), Black or African American (BL), Native Hawaiian or other Pacific Islander (NH), White (WH) and Multiple (MU).

There are five study periods defined in section 7.1 of the protocol:

- Screening Period
- Induction Dosing Period

- Maintenance Dosing Period
- Extension Period- Induction
- Extension Period- Maintenance
- Follow Up Period

Table 1 gives the treatment groups to be displayed for each treatment period and analysis population post implementation of protocol amendment (a). NOTE: “LY3074828” will be included in treatment group names in the statistical reports where possible.

Table 1 Treatment Groups for Each Treatment Period and Analysis Population

Treatment Period	Analysis Population	Treatment Groups	Abbreviation	Between Group comparison (when applicable)	Overall Comparison(when applicable)
Induction Dosing Period	ITT, Safety	600 mg LY3074828 IV 200 mg LY3074828 TDM IV 50 mg LY3074828 TDM IV LY3074828 Total Pbo IV	600 mg IV 200 mg TDM IV 50 mg TDM IV LY T total Pbo IV	600 mg IV vs Pbo IV 200 mg TDM IV vs Pbo IV 50 mg TDM IV vs Pbo IV	600 mg IV 200 mg TDM IV 50 mg TDM IV Pbo IV
Maintenance Dosing Period	Induction Responders	200 SC LY3074828 Q4W 200 SC LY3074828 Q12W LY3074828 Total Pbo SC	200 SC Q4W 200 SC Q12W LY T total Pbo SC	200 SC Q4W vs 200 SC Q12W	No Overall Comparison
Extension Period Induction	All enrolled in Extension Period- Induction	600 mg LY3074828 IV 1000 mg LY3074828 IV Total	600 IV 1000 IV Total	600 mg IV vs 1000 mg IV	No Overall Comparison
Extension Period Maintenance	All enrolled in Extension Period- Maintenance	200 mg LY3074828 SC Q4W	200 SC Q4W	No Between-Group Comparison	No Overall Comparison

Note- Patients who received 600mg IV Extension dosing prior to the protocol amendment will be summarized as 600mg IV. Patients who received 1000mg IV Extension dosing after to the protocol amendment will be summarized as 1000mg IV.

Safety summaries will only compare LY Total to Pbo in Induction.

All summary tables will be presented by treatment group. Where applicable, data will be summarized by treatment group by study visit. Summaries and analyses will be presented

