Compliance	Programmable (clinical database)	Patient received a dose adjustment but was not eligible for a dose adjustment per protocol.	Only patients in the 50 mg and 200 mg induction treatment arms are eligible for adjustment.
Compliance	Programmable (clinical database)	Patient experienced a TDM dose decrease.	Protocol specified that patients will not experience a dose decrease on the basis of drug concentrations (protocol section 9.5).
Compliance (Missed Dose)	Programmable (clinical database)	Dose missed or administered outside of the protocol defined visit window.	Out of window is defined as +/- 14 days.
Category: Study Procedures			
Subcategory:			
Excluded Conmeds	Non Programmable (Monitoring)	103 = Excluded Medication Used	
Visit Schedule Criteria	Non Programmable (Monitoring)	101 = Visit/ Procedure out of window	

Other	Non Programmable (Monitoring)	102 = Visit/ Procedure not done	
Category: Other			
Subcategory:			
Other	Non Programmable (Monitoring)	106 = Other protocol deviation	
Other	Non Programmable (Monitoring)	208 = Other regulatory deviation	
Category: Administrative/Oversight			
Subcategory:			
Improper Conduct of Assessments	Non Programmable (Monitoring)	207 = Procedure performed by non-delegated personnel	
Reg/Ethic Approvals	Non Programmable (Monitoring)	204 = IRB approval not obtained prior to screening	
Reg/Ethic Approvals	Non Programmable (Monitoring)	205 = IRB approval expired	
Category: Safety			
Subcategory:			
SAEs	Non Programmable (Monitoring)	206 = Failure/delay in SAE reporting	

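### Dose-adjustment status is tested as a subgroup although it is set after randomisation and cannot be 'yes' on placebo, so it gives no valid comparison with placebo

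*SAP*

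**What the plan says.** SAP section 6.15.1 names Week 12 clinical remission as the outcome for subgroup analysis and includes "TDM adjustment status: yes or no" in a list otherwise made up of demographic, regional, treatment-history and baseline factors. One rule covers the whole list. A logistic model with treatment, subgroup and their interaction is fitted, and the interaction is tested at 0.10. Then "Treatment group differences will be evaluated within each category of the subgroup using" Fisher's exact test, whatever the interaction shows. The only brake is on size: if any group "is less than 10% of the total population, only descriptive statistics will be provided for that subgroup".

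On where the factor comes from, the same section says "TDM adjustment status will be determined by utilizing responses in the Exposure Based Dose Adjustment eCRF page". It does not say how placebo and 600 mg patients are coded.

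Other places fix who can be adjusted, when, and what is compared:

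- Protocol section 9.5: patients in the 50 mg and 200 mg groups "will have their doses increased at the Week 4 (Day 29) and Week 8 (Day 57) visits if the projected trough concentrations" fall below set thresholds.
- Protocol section 7.1: "The 600-mg dose arm will remain at a fixed dose during the induction period".
- SAP section 6.16, Table 9: "Only patients in the 50 mg and 200 mg induction treatment arms are eligible for adjustment". An adjustment in any other patient is an important protocol deviation.
- SAP section 6.1, Table 1: the induction comparisons are each dose against placebo, including "200 mg TDM IV vs Pbo IV 50 mg TDM IV vs Pbo IV".

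**The concern.** A subgroup test of treatment effect needs a factor that treatment cannot influence and that can take each value in every arm. Adjustment status fails on both counts. It is set four to eight weeks after randomisation from drug concentration, and under the protocol it cannot be *yes* on placebo or 600 mg.

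The selection may well be prognostic. Protocol section 9.5 itself suggests that low exposure may contribute to lack of efficacy, and says the thresholds were chosen to pick out patients with lower than expected exposure. A p-value for 50 mg or 200 mg against placebo among unadjusted patients would then mix drug effect with that selection. A reader could take it as evidence about whether patients who did not need adjustment benefit.

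**Working it through.** **Inputs.** 240 patients, 60 per arm, remission 30% on drug and 7.5% on placebo (protocol 12.1, SAP 5.2); about 40% adjusted at Week 4 and a smaller share at Week 8 (protocol 9.5, read here as a share of the 50 mg and 200 mg arms); 10% rule and tests (SAP 6.15.1). The 50% ever adjusted, the ratio r and the early-leaver shares d used below are assumptions; the documents give none of them.

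**The plan's own figure.** With 60 per arm, 30% vs 7.5%, pooled chi-square and two-sided 0.05, power is 89.4%. This agrees with the stated 89% and is not in dispute.

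**Size of the categories.** At 40%: 0.40 × 60 = 24 per adjustable arm, so *yes* = 48, and 48/240 = 20%. At 50%: 30 per arm, 60/240 = 25%. Taking the total population as 240, the 10% rule applies only below 24 patients, that is below 24/120 = 20% of the two adjustable arms. It would not be triggered.

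**Expected cells at 40% adjusted, placebo and 600 mg coded *no*.**

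| | Placebo | 50 mg | 200 mg | 600 mg |
|---|---|---|---|---|
| *yes* | 0 | 24 | 24 | 0 |
| *no* | 60 | 36 | 36 | 60 |

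**What the model can estimate.**

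- Placebo and 600 mg coded *no*: the model has 1 intercept + 3 treatment + 1 status + 3 interaction = 8 columns, but only 6 filled cells, so its rank is 6. The main-effects part has rank 5, which leaves 1 of 3 interaction terms: the status effect at 50 mg against that at 200 mg. No interaction against placebo is estimable.
- Placebo and 600 mg given no status: 1 + 1 + 1 + 1 = 4 columns and 4 cells, full rank. This is a 2 × 2 analysis of 50 mg against 200 mg by status, with no placebo contrast in either category.

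**Selection bias in *no*, if placebo is coded *no* (illustration).** Let a be the share adjusted and r the remission rate of placebo patients who would have been adjusted, relative to the other placebo patients. The proper comparator for unadjusted drug patients is the placebo patients who would not have been adjusted. Their rate is 0.075/((1 − a) + a·r), and the bias is that rate minus 7.5%.

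| r | a = 0.4 | bias (points) | a = 0.5 | bias (points) |
|---|---|---|---|---|
| 0 | 0.075/0.60 = 12.5% | +5.0 | 0.075/0.50 = 15.0% | +7.5 |
| 0.375 | 0.075/0.75 = 10.0% | +2.5 | 0.075/0.6875 = 10.9% | +3.4 |
| 1 | 7.5% | 0 | 7.5% | 0 |
| 2 | 0.075/1.40 = 5.4% | −2.1 | 0.075/1.50 = 5.0% | −2.5 |

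For an ineffective drug at a = 0.4 (36 against 60 patients), the chance that Fisher's test is significant in favour of drug is 1.9% at r = 1, 4.0% at r = 0.5 and 10.0% at r = 0.

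**Early leavers pull the other way.** Patients who leave before Week 4 cannot be adjusted and count as non-responders (SAP 6.4.1). Let a share d of the arm leave early and be coded *no*, let a be the share adjusted among those remaining, and let status otherwise be unrelated to outcome. With 30% remission in the arm, the rate in *no* is 0.30(1 − a)/((1 − a) + a·d).

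- a = 0.4: 0.18/0.62 = 29.0% at d = 0.05 (−1.0 point); 0.18/0.64 = 28.1% at d = 0.10 (−1.9).
- a = 0.5: 0.15/0.525 = 28.6% at d = 0.05 (−1.4); 0.15/0.55 = 27.3% at d = 0.10 (−2.7).

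**The case against.** The subgroup text does not name placebo, and the comparison column of Table 1 applies only where applicable. With no placebo patients in *yes*, the analyst would simply make no such comparison there. That is fair for *yes*, but it does not help in *no*, where placebo patients would be present and the test would run.

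The misleading p-value arises only if placebo is coded *no*, and the eCRF page that decides this is not among the documents. This stands as a condition. The other coding leaves no placebo contrast at all, so neither rescues the analysis. Nor is 50 mg against 200 mg by status a randomised contrast, since the thresholds differ (0.5 and 2.0 µg/mL).

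The bias figures rest on assumed values and include zero. This also stands: they show what is possible, and the structural fault does not depend on them. Reading the 40% or 50% as a share of the whole arm changes the early-leaver figures to −1.1 to −2.2 points and −1.6 to −3.3 points, at most 0.6 points different. If placebo and 600 mg have no status, the total population for the 10% rule might be 120 and the limit 12; 48 patients still exceed it.

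Finally, this is one exploratory subgroup, without multiplicity control and not certain to appear in the report. That limits the consequence but does not make the specified test valid. 600 mg against placebo in *no* does remain randomised, because both arms fall wholly in that category.

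**Conclusion.** The concern holds. As written, SAP 6.15.1 prespecifies tests that cannot give a valid comparison of 50 mg or 200 mg with placebo by adjustment status under either possible coding. *Yes* is expected to hold about 20% of patients (25% if half are ever adjusted), and none of them on placebo unless there is a protocol deviation. With placebo and 600 mg coded *no*, one of three interaction terms is estimable. The illustrated selection bias in *no* runs from +7.5 to −2.5 points, with a further −1.0 to −2.7 points possible from early leavers. The sign and size depend on the assumed r, adjustment share and dropout.

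The damage is confined to this subgroup result. The primary intent-to-treat test, the testing hierarchy and the 89% power are untouched.

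**What to change.** Remove adjustment status from the list of subgroups that are tested in SAP 6.15.1. Report Week 12 remission by status descriptively, within the 50 mg and 200 mg arms only, with no test against placebo and a note that the categories are formed after randomisation. State how the eCRF codes patients who leave before Week 4, and likewise those who leave between Weeks 4 and 8 and those who kept their previous dose because the sponsor could not supply an adjustment (protocol 9.5). Leave the effect of exposure to the exposure-response modelling already planned in protocol 12.2.7.

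The cost is one deleted list item and one descriptive table, with no extra data. SAP version 3.0 was approved after unblinding, so the change and its reason should be recorded in the SAP revision history and the clinical study report.

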5.2. Determination of Sample Size

Approximately 240 patients will be randomized to 1 of 4 double-blind treatment regimens to evaluate the primary endpoint. Patients will be randomized to placebo, 50 mg LY3074828 Therapeutic Drug Monitoring (TDM), 200 mg LY3074828 TDM, or the 600 mg LY3074828 fixed-dose treatment group in a 1:1:1:1 ratio (60 patients per arm). The randomized patients will be comprised of approximately one-third biologic-naïve patients (~20 per arm) and approximately two thirds patients who have been exposed previously to at least 1 biologic agent (~40 per arm).

Assuming LY3074828 and placebo clinical remission rates of 30% and 7.5% respectively (a difference of 22.5%) and given 60 patients per treatment arm, each pairwise comparison testing

the superiority of LY3074828 to placebo will have 89% power via chi-square test with a two-sided 0.05 significance level.

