separately for the Induction Dosing Period and the Maintenance Dosing Period. Summaries and analyses will be also presented for the Extension Period.

By-patient listings will be sorted by treatment allocation, site and visit. Numeric data will be listed to the same number of decimal places as recorded on the eCRF. For derived variables, the number of decimal places will be listed as specified. The decimal points will be aligned in the data listings. For the tables and listings in the appendices, "Page x of X" will appear on each page.

By-patient listing will be generated for each SDTM dataset. If necessary, separate listing for derived variables (that are derived from the SDTM datasets) will be generated. Wherever applicable, listings will include the period of the study during which the event or measurement occurred.

Efficacy analyses will be conducted on the Intent-to-Treat (ITT) population. All safety analyses will be conducted on the Safety Population. These populations are defined in section 6.2.

Patients will be analyzed according to the treatment to which they were assigned regardless of any errors of dosing.

All tests of treatment effects will be conducted at a 2-sided alpha level of 0.05 unless otherwise stated. Unless otherwise specified, no multiplicity adjustment will be considered for planned analyses.

For all efficacy and health outcomes analyses, baseline is defined as the last non-missing assessment recorded on or prior to the date of first study drug injection at Week 0 (Visit 2). However, placebo patients who enter the Extension Period will have their baseline reset. Their new baseline will be defined as the last non-missing assessment on or prior to the date of first injection of study treatment at Week EW0 (Extension Visit 1).

Unless otherwise specified, variables will be analyzed in the original scale on which they are measured. However, if it is deemed more statistically appropriate, a transformation, such as to the logarithmic scale, may be applied before analysis. The parametric approach will be employed by default for statistical analysis except when nonparametric analysis, such as by a rank-based method, is assessed to be more fitting.

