6.3. Adjustments for Covariates

The randomization at the beginning of the Induction Period is stratified by previous biologic therapy: previous exposure to biologic therapy for treatment of UC, biologic naïve to biologic therapy for treatment of UC. Unless otherwise specified, all efficacy and health outcome analyses will include the stratification factors in the model.

The re-randomization at the beginning of the Maintenance Period of patients who took LY3074828 during the Induction Period and were responders at Week 12 (Visit 7) is stratified by the Week 12 level of clinical response: Clinical Remission or Clinical Response. Unless otherwise specified, all efficacy and health outcomes analyses using the Maintenance Dosing Period Primary population will include the re-randomization factor of Week 12 level of response in the model.

Unless otherwise specified, analyses will be performed utilizing the methodology and covariates described in section 6.1.

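### The subgroup interaction model in SAP 6.15.1 leaves out the randomisation stratum without a reason, and the within-category Fisher tests are conservative: a minor, inexpensive improvement

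*SAP*

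**What the plan says.** SAP 6.15.1 analyses Week 12 clinical remission in each listed subgroup in two steps.

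- **Interaction.** The SAP states that "a logistic regression model with treatment, subgroup, and the interaction of treatment-by-subgroup included as factors will be used", with the interaction tested at 0.10. Previous biologic use enters only when it is the subgroup under study.
- **Within category.** "Treatment group differences will be evaluated within each category of the subgroup using" Fisher's exact test, whether or not the interaction is significant. Missing data are set to non-response. A category with under 10% of the population gets descriptive statistics only.

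The surrounding rules are these.

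- SAP 6.3: "Unless otherwise specified, all efficacy and health outcome analyses will include the stratification factors in the model". The induction stratification factor is previous biologic use.
- SAP 6.1: the main binary analysis is logistic regression with treatment, region and prior biologic experience. The secondary analysis is an exact CMH test stratified by previous biologic use, and Fisher's test is kept for use where needed.
- SAP 6.1, on the level: "All tests of treatment effects will be conducted at a 2-sided alpha level of 0.05 unless otherwise stated".
- SAP 6.6: multiplicity is controlled only for the three primary comparisons.

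The SAP states no power or true error rate for the subgroup tests.

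**The concern.** The subgroup step uses a different method from the analysis it is meant to illuminate, and the SAP does not say why. Two separate things follow.

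First, leaving a prognostic factor out of a logistic model costs some power. Previous biologic use was judged important enough to stratify on and is recorded for every patient, so including it is easy.

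Second, Fisher's test is strongly conservative when events are few and arms are small. SAP 5.2 plans about 20 biologic-naive and 40 biologic-exposed patients per arm, with a placebo rate of 7.5%. A within-category p-value will then often exceed 0.05 even when the full design effect is present. SAP 6.15.1 asks for that test but does not ask for a rate difference with a confidence interval in each category, which would show how little a non-significant result says.

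**Working it through.** **Inputs from the documents.** SAP 5.2: "Assuming LY3074828 and placebo clinical remission rates of 30% and 7.5% respectively (a difference of 22.5%) and given 60 patients per treatment arm"; equal allocation; about 20 naive and 40 exposed per arm. Two-sided 0.05 for treatment effects (SAP 6.1); 0.10 for interaction (SAP 6.15.1). Per-arm sizes other than 20, 40 and 60, null rates other than 7.5%, and all stratum-specific rates are assumptions.

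**1. The plan's own figure.** SAP 5.2 says each comparison "will have 89% power via chi-square test with a two-sided 0.05 significance level". Power = Φ[(|Δ|√n − 1.96√(2p̄(1−p̄))) / √(p₁(1−p₁)+p₂(1−p₂))], with p̄ = (0.30+0.075)/2 = 0.1875. So (0.225×√60 − 1.96×0.5520)/0.5286 = (1.7428 − 1.0819)/0.5286 = 1.250, and Φ(1.250) = 0.894. The 89% reproduces, and it is for the chi-square without continuity correction.

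**2. Within-category tests.** For n per arm, every pair of counts (a, b) is enumerated, and the rejection probability is the sum of Bin(a; n, p₁)×Bin(b; n, p₂) over the pairs that reject.

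| n per arm | Power, Fisher | Power, chi-square | Loss (points) | Fisher size at 7.5% | Fisher size at 10% | Chi-square size at 7.5% / 10% |
|---|---|---|---|---|---|---|
| 20 | 33.1% | 46.3% | 13.3 | 0.6% | 1.2% | 2.6% / 3.9% |
| 25 | 41.7% | 57.3% | 15.6 | 0.4% | 0.9% | 3.8% / 4.9% |
| 30 | 49.3% | 63.5% | 14.2 | 0.5% | 0.9% | 4.7% / 5.4% |
| 40 | 68.2% | 77.0% | 8.9 | 1.0% | 1.7% | 5.7% / 5.9% |

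Power is at 30% against 7.5%; losses are taken before rounding. To show the mechanism: at 20 per arm, 6 remitters against 1 gives a chi-square of 25/(40×0.175×0.825) = 4.33, which rejects, but a Fisher p-value of 0.091. Fisher's test needs 7 against 1.

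**3. How much is due to the stratum.** Simulation (20,000 runs) with one-third naive, placebo rates 12.5% naive and 5% exposed, and active rates 42% and 24%. These average to (12.5+2×5)/3 = 7.5% and (42+2×24)/3 = 30%. Uncorrected CMH stratified by previous biologic use has power 47.7%, 64.5% and 78.0% at 20, 30 and 40 per arm. Against the chi-square column this is 1.4, 1.0 and 1.0 points more. The rest of the gap is Fisher's test.

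**4. A different comparator.** Logistic regression with the stratum and a Wald test, under the same assumptions (5,000 runs), has power 24%, 37%, 52% and 70% at 20, 25, 30 and 40 per arm. Fisher's test has 33%, 42%, 49% and 68%: better at 20 and 25, and 2 to 3 points worse at 30 and 40. The likelihood-ratio version reaches about 51–79%, but its error rate is about 8–9%.

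**5. Interaction model.** Likelihood-ratio test at 0.10, 3,000 runs, without and with the stratum as a main effect, by assumed odds ratio for the stratum: 38.8% and 38.6% (odds ratio 1); 39.4% and 41.1% (0.5); 37.5% and 39.8% (0.33); 38.1% and 41.9% (0.2). Each figure has a simulation standard error of √(0.39×0.61/3000) = 0.9 points. Across other assumed settings the gain ran from about 1 to 7 points.

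A repeat with 20,000 runs used two categories of 30 per arm, one-third naive, placebo 7.5% in both, and active 45% and 15%. It gave 38.3% and 38.8% (odds ratio 1), 38.0% and 39.3% (0.5), and 37.4% and 43.0% (0.2). With no interaction (placebo 15% and active 30% in both categories), the error rate went from 11.6% to 11.7%, 11.5% to 12.0%, and 9.9% to 11.7%. At the strongest assumed effect, then, part of the gain reflects an error rate returning to its level without a prognostic factor.

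**The case against.** The strongest reply is that nothing is broken. SAP 6.3 opens with an exception, 6.15.1 uses it, and 6.1 foresees Fisher's test. A reader might infer a breach of the covariate rule; the text does not support that. What remains is an unexplained choice.

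A reader might also infer that dropping the stratum causes the 9 to 16 point loss. It does not. Those figures concern the within-category tests and not the interaction model, and the stratum accounts for at most about 1.4 points under the assumed rates. In the biologic-naive and biologic-exposed categories themselves, nothing is dropped.

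Nor is Fisher's test shown to be weaker than the plan's primary method. The SAP does not say which logistic test it uses, and against a Wald test Fisher's test is better in the smallest categories. The loss exists only against a named alternative. The exact CMH in SAP 6.1, being exact, would share some of the conservatism; the gains here are for the version without exact calculation or continuity correction.

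Finally, conservatism errs towards fewer false subgroup claims, which has some merit across many unadjusted subgroup tests at three doses. That stands, and it keeps the point minor. A claim that absent effects will be over-reported would assume that readers take non-significance as no effect; the SAP does not say so.

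**Conclusion.** The point holds as a small improvement in two separate parts.

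- **Interaction model.** Including the stratum is worth about 1 to 7 points of power if previous biologic use is prognostic at the assumed odds ratios, and makes practically no difference if it is not. The documents give no odds ratio.
- **Within-category tests.** The conservatism and the 9 to 16 point loss are firm for 20 to 40 per arm at the SAP's 30% and 7.5%, against an uncorrected chi-square or CMH. An error rate of 1–2% should not be read as the result at the plan's own placebo rate; it belongs to the assumed 10%.

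The subgroup tests are exploratory, carry no multiplicity control and drive no stated decision. A true error below 5% is not a validity error, and the primary analysis is unaffected.

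**What to change.** **Main change.** In SAP 6.15.1, add previous biologic use as a main effect to each subgroup logistic model, except where it is the subgroup itself, or state why it is left out. The cost is one line of text and one model term. The model would still differ from the primary one, which also contains region.

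**Optional second change.** Report the remission-rate difference with a 95% confidence interval in every category that is tested. Replace Fisher's test by a CMH test without continuity correction, stratified by previous biologic use (a plain chi-square within the previous-biologic categories), or by Fisher's mid-p. Keep Fisher's test where a stratum is empty.

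The cost is wording and programming, plus a known size penalty: the uncorrected chi-square reaches about 5.9% at 40 per arm, which is the planned biologic-exposed size and not a sparse corner. Mid-p gains less (10.4, 8.2, 11.7 and 4.9 points at 20, 25, 30 and 40 per arm), but its error stays at or below about 3.1% at the 7.5% and 10% rates. Statisticians may reasonably differ on this swap; the intervals are worth adding whichever test is kept.
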